3.1 Basic Information

3.1.1 Haemophilia A

Haemophilia A is a recessive X-linked congenital bleeding disorder caused by mutations in the coagulation factor VIII gene on the long arm of the X-chromosome. According to the World Federation of Haemophilia (WFH), there are globally 320,000 – 340,000 patients with haemophilia A of which only approximately one quarter receives adequate care¹.

With a deficiency or absence of FVIII, activation of coagulation factor X becomes severely impaired, and consequently, the thrombin burst becomes delayed and insufficient for normal haemostasis². The haemostatic plug formed in these patients is, if formed, fragile and easily dissolved by normal fibrinolytic activity, leading to impaired haemostasis, prolonged bleeding episodes and re-bleeding. The bleeding episodes in patients with severe haemophilia A are typically spontaneous or after mild trauma in joints, muscles and soft tissues. The bleeding episodes often occur in the muscles and joints of the elbows, knees and ankles, causing acute haemarthrosis. In repeated cases this is followed by synovitis in the affected joint. Recurrent bleeding episodes in the same location, may lead to chronic arthropathy, muscular atrophy and deformities³. Bleeding episodes may occur in all parts of the body including life-threatening bleeding episodes in the central nervous system (CNS), throat, neck, gastrointestinal tract, retroperitoneum or external injuries. As the Human Immunodeficiency Virus (HIV) and Hepatitis C (HCV) epidemics have subsided, the most serious complication to haemophilia treatment is inhibitor development. Inhibitors are allogeneic antibodies to FVIII that reduce or eliminate the activity of FVIII proteins in clotting factor concentrates. This condition develops in as many as 30–35% of previously untreated patients (PUPs) with severe haemophilia A^{4,5}. Hence, the risk of inhibitor development related to the individual product should be initially evaluated in PTPs as these patients have been exposed to previous FVIII products and considered to be at a low risk of developing inhibitors and therefore the most suitable for trial population.

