5.3 Treatment of Patients

Approximately 150 patients are planned to be screened in order to dose approximately 132 patients in the trial out of which 105 patients are expected to complete the prophylaxis part of the trial and a minimum of 10 patients are expected to complete approximately 6 months in the on-demand part of the trial.

The two initial doses of N8-GP will be administered in a hospital setting in order to observe for adverse reactions. Thereafter, home treatment can be initiated. All patients must previously have received at least 150 doses of FVIII and must be familiar with or instructed in home treatment of both prophylaxis and treatment of bleeding episodes.

A severe bleed should be treated immediately at home and the haemophilia site must be contacted without delay for further instructions and/or transport to the site.

The following medications are not allowed during the course of the trial until after the EOT visit:

- Bypassing products: rFVIIa, pd-PCC and pd-aPCC
- Coagulation Factors containing products: FVIII, FIX and FVII other than N8-GP.
- Anti-coagulants such as Heparin and vitamin-K antagonists. Heparin is allowed for sealing of central venous access ports

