5.3.2 Treatment of Bleeding episodes

A treatment requiring bleeding episode is in this trial defined as a bleed that require treatment with a coagulation factor product e.g. N8-GP. If a patient experiences a treatment requiring bleed it must be treated as soon as it is identified (refer to Section [8.2.1](#)). The Investigator must always be contacted in case of a severe bleed and the patient should visit the site within 24 hours.

Mild/moderate bleeding episodes can be treated at home without contacting the site. For definition of the severity of a bleed please refer to section [8.2.1.1](#).

For the treatment of bleeding episodes, doses will be based on World Federation of Haemophilia (WFH) guidelines¹ (see Section [8.2.1](#)). For treatment of a bleed all on demand and prophylaxis patients will be treated with doses between 20-75 U/kg BW (the recommended standard dose will be 50 U/kg). Due to individual patient's bleeding pattern during the trial, an adaptation in dosing regimen to 50 U/kg twice weekly will be permitted at the investigator's discretion. If the dosing regimen is changed to twice weekly, doses should be separated by at least 3 calendar days and no more than 4 calendar days.

The dose for treatment of bleeding episodes is aimed to achieve an expected post injection level of at least 0.50 U/mL of FVIII.

Any dose used for treatment of a known active bleed must be recorded as treatment of bleed and not as prophylaxis treatment. When the bleed has resolved, the patient can resume the prophylaxis treatment.

If a dose for treatment of a bleed is taken, the next prophylaxis dose should follow the original dosing scheme and not be altered by the additional treatment of bleed administration. If a bleed occurs on the same day as the planned prophylaxis, the dose must be registered for the bleed and not as prophylaxis.

Number of doses and frequency of dosing is decided by the Investigator in relation to the particular bleed. The maximum dose to be administered to a patient within 24 hours (hrs) is 200 U/kg BW. The dose is recommended to be divided and only considered under exceptional circumstance such as serious trauma or severe bleeding episodes.

If a haemostatic response cannot be achieved after 48 hours using adequate doses of N8-GP treatment when treating bleeding episodes, another FVIII product may be selected at the discretion of the Investigator. The use of other FVIII products will result in withdrawal of the patient.

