8.2.1.1 Definition of Severity of Bleeding episodes

- **Mild/Moderate:** Bleeding episodes that are uncomplicated joint bleeds, muscular bleeds without compartment syndrome, mucosal- or subcutaneous bleeds
- **Severe:** All intracranial, retroperitoneal, iliopsoas and neck bleeds must be categorised as severe. Muscle bleeds with compartment syndrome and bleeds associated with a significant decrease in the haemoglobin level (>3g/dl) should also be reported as severe. These bleeding episodes must be treated immediately or at the local emergency room and the trial personnel must be contacted. The details of severe bleeding episodes must be entered in the eDiary or if the patient is unable to fill in the e-Diary or hospitalized, the Investigator or trial personnel can enter the data in the eCRF as an unscheduled visit. Traumatic bleeds at other locations than described above can always be considered severe at the investigators discretion.

8.2.1.2 Definition of Haemostatic Response:

- **Excellent:** abrupt pain relief and/or unequivocal improvement in objective signs of bleeding within approximately 8 hours after a single infusion.
- **Good:** definite pain relief and/or improvement in signs of bleeding within approximately 8 hours after one infusion, but possibly requiring more than one infusion for complete resolution
- **Moderate:** probable or slight beneficial effect within approximately 8 hours after the first infusion; usually requiring more than one infusion
- **None:** no improvement, or worsening of symptoms

Classification of a bleeding episode

- Spontaneous, traumatic, re-bleed, minor surgery

Classification of re-bleed will be performed by the trial statistician at the time of the statistical analysis according to the following criteria: A re-bleed is defined as a worsening of symptoms in the same location after an initial period of improvement, either on treatment or within 72 hours after stopping treatment. If a bleed occurs in the same location later than 72 hours after stopping the treatment it is considered a new bleed.

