5.3.2 Treatment of Bleeding episodes

A treatment requiring bleeding episode is in this trial defined as a bleed that require treatment with a coagulation factor product e.g. N8-GP. If a patient experiences a treatment requiring bleed it must be treated as soon as it is identified (~~refer to Section 8.2.1~~).

...

~~For the treatment of bleeding episodes, doses will be based on World Federation of Haemophilia (WFH) guidelines¹ (see Section 8.2.1). For treatment of a bleed, all on demand and prophylaxis patients will be treated with doses between 20-75 U/kg BW (the recommended standard dose will be 50 U/kg). to achieve a desired dose level based on the severity and location of the bleeding episode. Each unit of N8-GP will raise the FVIII level with approximately 2%. For recommended dose levels see table 1. Further guidance on the treatment of bleeds may be found in WFH guideline¹.~~

The dosage is calculated by multiplying the patient's weight in kilograms by the factor level desired multiplied by 0.5. This will indicate the number of N8-GP units required.

Example: 50 kg x 40 (% level desired) x 0.5 = 1 000 units of N8-GP.

Table 2–1 Guide for dosing in bleeding episodes

Type of haemorrhage	Desired level	Recommended dose
Joint, muscle (except iliopsoas)	40% - 60%	20 - 30 U per kg
CNS/head, Throat and neck, Gastrointestinal, Iliopsoas	80% - 100%	40 – 50 U per kg

Based on recommendations WFH guidelines.

The effect of initial N8-GP dose on the clinical symptoms should be closely monitored and the need for a second dose should be evaluated within 8 hours after the initial N8-GP dose. If further doses are considered necessary to treat the bleeding episode, the patient is recommended to contact the investigator.

The maximum dose to be administered to a patient within 24 hours (hrs) is 200 U/kg BW. The dose is recommended to be divided and only considered under exceptional circumstance such as serious trauma or severe bleeding episodes.

Age and body weight are markedly correlated in children and adolescents. As the dosing of N8-GP takes body weight into account no further adjustment is needed in the adolescents included in this trial.

Due to individual patient's bleeding pattern during the trial, an adaptation in dosing regimen to 50 U/kg twice weekly will be permitted at the investigator's discretion. If the dosing regimen is changed to twice weekly, doses should be separated by at least 3 calendar days and no more than 4 calendar days.

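### Section 8.2.1.1 leaves gastrointestinal, spinal and, on one reading, throat bleeds off the list of severe sites, so a patient treating such a bleed at home has no clear duty to contact the site

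*Protocol*

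**What the plan says.** **Severity.** Protocol 8.2.1.1 gives a list by site: "All intracranial, retroperitoneal, iliopsoas and neck bleeds must be categorised as severe". Two further routes to severe depend on the consequence: compartment syndrome for muscle bleeds, and a haemoglobin fall of more than 3 g/dl for a bleed at any site. A discretion sentence follows: "Traumatic bleeds at other locations than described above can always be considered severe at the investigators discretion". Besides uncomplicated joint bleeds, the mild/moderate class covers "muscular bleeds without compartment syndrome, mucosal- or subcutaneous bleeds". The word mucosal carries no limit on site.

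**Conduct at home.** Section 5.3 says: "A severe bleed should be treated immediately at home and the haemophilia site must be contacted without delay". Section 5.3.2 adds: "The Investigator must always be contacted in case of a severe bleed and the patient should visit the site within 24 hours". It then lets patients treat mild/moderate bleeds at home without contacting the site, and refers to 8.2.1.1 for the class. Amendment 2 added one more contact sentence: "If further doses are considered necessary to treat the bleeding episode, the patient is recommended to contact the investigator".

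**How the protocol views these sites elsewhere.** Section 3.1.1 speaks of "life-threatening bleeding episodes in the central nervous system (CNS), throat, neck, gastrointestinal tract, retroperitoneum or external injuries". The dosing guide that Amendment 2 placed in 5.3.2 gives its upper row (desired level 80-100%, 40-50 U/kg) to "CNS/head, Throat and neck, Gastrointestinal, Iliopsoas". None of the amendments in the document changes 8.2.1.1.

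**The concern.** The severity class is more than a label applied afterwards. It decides, when the bleed starts, whether the patient must call and be seen within 24 hours, and under 8.2.1 it decides who is responsible for treatment. If sites that the protocol itself counts as life-threatening are missing from the severe list, the contact rule does not clearly reach them.

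There is a secondary effect in the extension. Amendment 14 requires a patient on every-7-day dosing to return to every-4-day dosing after two or more spontaneous bleeds in 8 weeks, or after one severe bleed requiring hospitalisation. The second criterion uses the same definition of severe.

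**Working it through.** The plan gives no figure to reproduce. The check sets the lists side by side and follows each bleed through the contact rule.

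**1. Sites in 3.1.1 against the severe list in 8.2.1.1**

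| Site in 3.1.1 | Severe by site in 8.2.1.1? |
|---|---|
| Neck | yes |
| Retroperitoneum | yes |
| CNS | partly (intracranial only; spinal not listed) |
| Throat | no, unless neck includes throat |
| Gastrointestinal tract | no |
| External injuries | only through the discretion sentence for traumatic bleeds |

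Count: 2 full + 1 partial + 2 absent + 1 by discretion = 6. If neck includes throat: 3 + 1 + 1 + 1 = 6.

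**2. Upper dosing row against the same list**

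The row has four entries. Iliopsoas is covered, CNS/head partly, throat and neck partly, and gastrointestinal not at all: 1 full + 2 partial + 1 absent = 4. If neck includes throat: 2 + 1 + 1 = 4.

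**3. What the contact rule gives at onset**

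- *Mucosal gastrointestinal or throat bleed:* it fits the mild/moderate wording, so 5.3.2 can be read as allowing home treatment without contact.
- *Spinal or non-mucosal gastrointestinal bleed:* it appears in neither class, so 5.3.2 points to a definition that gives no answer.
- *Haemoglobin route:* a fall above 3 g/dl makes any of these severe, but a patient at home cannot know this before a blood test.
- *Amendment 2 sentence:* it is a recommendation, and applies only if further doses are thought necessary.
- *Contact for every bleed:* Amendment 6 makes this mandatory only between visits 2a and 2b.

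**4. Switch-back from every-7-day dosing**

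Take one spontaneous gastrointestinal bleed that leads to hospitalisation, with a haemoglobin fall of at most 3 g/dl.

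- Criterion 1 (two or more spontaneous bleeds in 8 weeks): 1 < 2, not met.
- Criterion 2 (severe and hospitalised): met if rated severe, not met if rated mild/moderate.

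Either criterion is enough. The bleed meets 1 of 2 if rated severe, and 0 of 2 if rated mild/moderate. In the second case the switch is not mandatory on this bleed alone.

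**The case against.** The other side has several good points.

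- The lists in 3.1.1 and the dosing guide were not written as severity lists. The first is disease background and the second sets a target level. A site may warrant a higher dose without every bleed there being severe. This stands, and it is why the counts above show inconsistent wording and not risk.
- The dosing guide groups throat with neck, and neck is severe. That reading is possible, but 3.1.1 lists the two separately and a throat bleed may also be mucosal. Gastrointestinal and spinal bleeds stay unlisted on either reading.
- There are real safeguards. Patients or caregivers must be able to assess a bleed (inclusion criterion 6) and are instructed in how to do so (8.4.3). Patients carry a contact card (8.1), and unscheduled visits are available for any bleed. The need for a second dose is to be evaluated within 8 hours. These lower the risk, but none sets a duty to call at onset.
- Patient-facing text might say more. Amendment 6 describes the bleed guidance that it added to the consent form as covering only the time between visits 2a and 2b. The consent text itself is not available here, so fuller instructions cannot be ruled out.

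Three stronger readings are tempting, and the documents do not support them.

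- A reader might infer that limiting the discretion sentence to traumatic bleeds is what removes the contact duty. It is not: that sentence governs the investigator's later rating, and through it the switch-back rule, not what the patient must do at onset.
- A reader might infer that the investigator cannot rate a spontaneous gastrointestinal bleed as severe. Sections 8.2.1 and 8.4.3 make the investigator responsible for rating every bleed, and the site list sets a minimum.
- A reader might take the longest gap between scheduled visits in extension part 2 (12 + 2 = 14 weeks on every-4-day or on-demand treatment) as a possible delay in care. It is the longest time to a scheduled rating; the patient can call or attend at any time.

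**Conclusion.** The point holds as a gap in a safety definition. On the text, a mucosal gastrointestinal or throat bleed can be treated at home with no duty to contact the site, and a spinal or non-mucosal gastrointestinal bleed has no stated class. The protocol elsewhere regards these as dangerous sites.

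The switch-back effect is secondary. It needs a hospitalised spontaneous bleed, a haemoglobin fall of at most 3 g/dl and a mild/moderate rating. Even then, in part 1 the investigator may switch the patient at any time, and in part 2 clinical judgement overrides the rules. A life-threatening bleed is reported as an SAE whatever its class (12.1.3, Amendment 14).

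The documents give no frequency for such bleeds; the conclusion assumes that they are rare. Annualised bleeding rate counts treatment-requiring bleeds regardless of severity, and haemostatic response uses its own four-point scale, so no efficacy result changes. What is at stake is patient safety and the consistency of severity coding.

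**What to change.** In Protocol 8.2.1.1:

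1. Replace *intracranial* with *CNS (intracranial and spinal)*.
2. Add throat and gastrointestinal bleeds to the severe list.
3. Limit *mucosal* in the mild/moderate class to sites outside the throat and gastrointestinal tract, such as nose or mouth, so that no bleed falls in both classes.
4. Delete *Traumatic* from the discretion sentence, so that the later rating, and with it the switch-back rule, expressly covers spontaneous bleeds.

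Items 1 to 3 settle the duty to call; item 4 serves the rating. Section 5.3.1 can stay as it is, because a hospitalised bleed at any of the added sites would then meet its second criterion.

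The cost is a short amendment and a note to sites and patients. In use it means a few more calls and 24-hour visits, some for minor throat or gastrointestinal bleeds, and possibly a few more switch-backs. In extension part 1 each extra switch-back is imputed as a withdrawal (SAP 2.2.2) and counts toward the rule that closes the every-7-day arm at 15 of 30 patients (5.3.1, Amendment 14).

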8.3 Safety Assessments

8.3.1 Adverse Events

Monitoring of AEs will be performed from the first trial related activity (screening) to the EOT visit, according to the procedures described in section [12](#).

For recording of bleeding episodes, please refer to sections [8.2.1](#) and [12.1.3](#).

8.3.2 Antibody Assessments

Blood samples for assessment of antibody formation against N8-GP will be drawn at the screening visit, pre-dose of N8-GP administration at all visits (except visit 2b) and at the follow-up visit approximately one month after the End of Trial visit. Antibody samples will only be drawn from patients in the on-demand arm at Visit 3-13 if they have received treatment during the home treatment period since last visit. The samples will be analysed both using the Bethesda assay identifying inhibitory antibodies towards FVIII and using an assay capable of identifying the occurrence of any antibodies towards both rFVIII and N8-GP.

8.3.2.1 N8-GP antibody assay

Binding antibodies towards N8-GP and rFVIII in plasma will be analysed on an ongoing basis.

The presence of N8-GP binding antibodies will be determined by a radioimmunoassay and is validated according to internationally recognised guidelines and recommendations. For samples with a result above the cut-off the presence of anti-N8-GP antibodies will be confirmed in a confirmatory assay by addition of excess of unlabelled N8-GP. Furthermore, cross-reactivity to rFVIII will be measured in the confirmatory assay in parallel with excess of un-labelled rFVIII. Only samples positive in the confirmatory assay will be characterized as anti-N8-GP or anti-rFVIII antibody positive.

Levels of N8-GP binding antibodies will be compared to pre-dose samples throughout the trial. If a patient develops N8-GP binding antibodies and the incremental recovery value at that visit is less than 60% of screening value, a new inhibitor sample will be taken after a 7 days wash out period.

A patient that tests negative for inhibitors following a 7 days wash out will confirm a negative inhibitor test and the patient will continue in the trial.

This algorithm will not apply for those who enter the trial with positive N8-GP binding antibodies and will not be triggered more than twice for an individual patient. Furthermore, a 7 days wash out period will only be applied if the 96 hours wash out is not sufficient to avoid drug interference in the inhibitor assay.

8.3.2.2 FVIII inhibitors

All patients will be examined for the development of FVIII inhibitors at scheduled visits. A positive inhibitor test is defined as ≥ 0.6 BU/mL. If FVIII inhibitor development is suspected (increased number of bleeding episodes, bleeding episodes difficult to treat, recovery and trough levels below expected values) during the course of the trial, additional inhibitor tests can be taken at Unscheduled Visits. All inhibitor tests must be analysed by the Central Laboratory.

In the event that a patient has a positive inhibitor test (≥ 0.6 BU/mL), the patient must attend an Unscheduled Visit as soon as possible or within 1 week after the result is available to take a confirmatory inhibitor test on a separately drawn sample. This second sample should preferably be taken prior to any change of treatment. At this Unscheduled Visit, a recovery test must also be performed. If the second inhibitor test is also positive, the patient must be withdrawn by discontinuing trial product and attending the EOT Visit within 1 week after the result is available.

A patient has inhibitor (≥ 0.6 BU/mL) if the patient has been tested positive for inhibitors at two consecutive test samples performed at the central laboratory preferably with no more than 2 weeks between the tests.

A follow-Up Visit must be scheduled 1 month after the EOT Visit and additional monthly follow-up visits may be arranged at intervals as long as clinically warranted up to 3 months after the EOT Visit.

All per protocol inhibitor laboratory samples are to be analysed in the central laboratory, and only these results will be used in the trial data analysis.

If the Investigator decides to send a sample for inhibitor testing to a local laboratory, the Investigator must also send a duplicate sample for inhibitor testing to the Central Laboratory. The data from the Central Laboratory will then be used in the official analysis. A positive inhibitor test must be reported as a MESI (please refer to section [12.1.2](#))

Blood samples for measurement of inhibitors towards FVIII will be analysed according to the Nijmegen modification of the Bethesda assay¹⁵. Any sampling for the inhibitor test must be performed at least 96 hours after last administration of N8-GP to allow for maximum wash-out of the drug.

An inhibitor test with a result ≥ 0.6 BU/ml will be considered as a positive inhibitor test. A patient is verified inhibitor positive if two independent samples from same patient are inhibitor positive (≥ 0.6 BU) – and the patient should discontinue the trial including an EOT Visit and FU Visits.

A patient having an initial positive inhibitor positive test and a second negative inhibitor test, will be reported as a MESI and continue in the trial.

If more than two patients are verified inhibitor positive an unscheduled Safety Committee Meeting will be called by Global Safety – and a decision whether to continue, modify or stop the trial will be made, see Section [12.5.3](#).

